3. CONVENTIONS

All summary tables, figures and data listings will be produced using SAS software 9.4 or above.

Summaries will be performed by treatment group, separately for Part A (crossover design) and Part B (parallel design).

Descriptive statistics will be used for all variables, as appropriate. Continuous variables will be summarised by the number of observations, mean, standard deviation, median, minimum, and maximum. For log-transformed data, the geometric mean, coefficient of variation (CV), median, minimum and maximum will be presented. No hypothesis testing will be conducted.

Categorical variables will be summarised by frequency counts and percentages for each category.

For AE summaries, the n and % of subjects with event, as well as the number of events, will be shown.

For all Part A endpoints, the last observation before the first dose of corresponding study treatment will be considered the baseline measurement unless otherwise specified. However, if an evaluable assessment is only available after randomisation but before the first dose of randomised treatment then this assessment will be used as baseline. For Part A, baseline for each treatment period will be defined as last observation before the first dose of study treatment (Period 1 Day -1 and Period 2 Day-1).

For Part B safety and PK endpoints, the last observation before dosing will be considered the baseline measurement unless otherwise specified. However, if an evaluable assessment is only available after randomisation but before the first dose of randomised treatment then this assessment will be used as baseline.

For Part B PD endpoints, the day -1 observation at each post-Capsaicin injection timepoint will be considered the baseline measurement for each corresponding day 1 post-Capsaicin timepoint, i.e., the baseline for day 1 15 minutes post-Capsaicin injection will be the day-1 15 minutes post-Capsaicin injection value. If a day-1 PD value at the 30-minute, 60-minute or 90-minute post-Capsaicin timepoints is missing for a subject, linear interpolation will be used to compute the missing value. If a subject's 120-minute post-Capsaicin value is missing, last observation carried forwards (LOCF) will be used instead. If a subject's 15-minute post-Capsaicin value is missing, next observation carried backwards (NOCB) will be used.

Assessments on the day of the dosing where neither time nor a nominal pre-dose indicator are captured will be considered prior to the dosing if such procedures are required by the protocol to be conducted before the dosing.

In all summaries change from baseline variables will be calculated as the post-treatment value minus the value at baseline. For Part A change from baseline will be calculated only for post-treatment evaluation during the corresponding Period (Days 1 to 3) and assigned to treatment according to treatment period (see Section X).

Data for Part A and Part B will be listed separately. All listings will be ordered by treatment sequence for Part A or by treatment for Part B and subject number and will include all available data including unscheduled data.

Unscheduled values will not be used for analysis. Assessments conducted at unscheduled visits will be listed.

Statistical Analysis Plan

There will be an interim analysis of PK for Part A and a final analysis of both parts.

Page layout of tables and listings in landscape mode:

- Page size: A4
- Margins:
 - Top = 2.54cm
 - Bottom = 2.54cm
 - Left = 2.54cm
 - Right = 2.54cm
 - Gutter = 0
 - Header (from edge) = 1.25cm
 - Footer (from edge) = 1.25cm
- Font:
 - Font size = 7.5
 - Font = Courier New

Statistical Analysis Plan

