A 12-lead ECG will be collected at the timepoints indicated in the Schedule of Assessments ([Appendix 1](#) and [Appendix 2](#)). The 12-lead ECG will be collected in triplicate, approximately 1 minute apart, at Screening, and within approximately 1-hour predose. Single readings will be collected at all other timepoints. 12-lead ECGs should be obtained after the subject has rested in the supine position for at least 5 minutes. In the event of an abnormal finding, recordings should be performed in triplicate. Triplicate recordings will be performed within 30 minutes of an abnormal finding. The ECG machine used should automatically calculate the HR and PR, RR, QRS and QTcF intervals.

For timepoints with multiple assessments:

- collect the ECG first,
- then vital signs,
- then the PK blood draw. The PK sample should be collected at the scheduled time postdose.

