15. APPENDICES

15.1. Appendix 1– Schedule of Assessments (Part A)

Schedule of Assessments Part A	Screening Up to 28 Days	Treatment Period 1 and Treatment Period 2 (minimum washout period of 7 days between periods)		Post-Study (5 to 7 days post final- dose)
		Day -1	Days 1 to 3	
Informed Consent	X			
Demography	X			
Inclusion/Exclusion Criteria ^a	X			
Medical History	X			
Urine Drugs of Abuse and Breath Alcohol Screen	X	X		
SARS-CoV-2 Test	X	X		
Serology	X			
Study Residency				
Admission		X		
Discharge			Day 3 (48 hours postdose)	
Non-Residential Visit	X			X
KLS-GABA/KLS Administration			Day 1	
Safety Assessments				
Physical Examination	X	X		X
Vital Signs (HR, BP and oral temperature) ^b	X		Predose, 1, 2, 4, 8, 24 and 48 hours postdose	X
12-Lead ECG ^c	X		Predose, 1, 4, 24 and 48 hours postdose	X
Clinical Laboratory Evaluations	X		Predose and 48 hours postdose	X
AE and Concomitant Medication Monitoring	X	X	Predose, 1, 2, 3, 4, 6, 8, 12, 24 and 48 hours postdose	X
Pharmacokinetic Assessments				
Blood Sampling ^d			Predose, 0.5, 1, 1.5, 2, 3, 4, 6, 8, 12, 16, 24, 36 and 48 hours postdose	

Abbreviations: AE – adverse event; BP – blood pressure; ECG – electrocardiogram; GABA – Gabapentin; HR – heart rate; KLS - Ketoprofen Lysine Salt; SARS-CoV-2 – severe acute respiratory syndrome coronavirus 2.

a A full check of inclusion/exclusion criteria will take place at screening. At all other days to which inclusion/exclusion criteria apply, only those particular inclusion/exclusion criteria will be checked

b Supine only.

c ECG assessments will be conducted within a ± 30 minute time window.
d Fourteen samples per subject will be taken per treatment period.

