15.2. Appendix 2– Schedule of Assessments (Part B)

Schedule of Assessments Part B	Screening Up to 28 Days	Screening 2 Prior to Day -1	Treatment Period		Post-Study (5 to 7 days post-final dose)
			Day -1	Day 1	
Informed Consent	X				
Demography	X				
Inclusion/Exclusion Criteria ^a	X				
Medical History	X				
Urine Drugs of Abuse and Breath Alcohol Screen	X		X		
SARS-CoV-2 Test	X		X		
Serology	X				
Study Residency					
Admission			X		
Discharge				12 hours postdose	
Non-Residential Visit	X				X
KLS-GABA/ KLS/Gabapentin/ Placebo Administration				X	
Safety Assessments					
Physical Examination	X				X
Vital Signs (HR, BP and oral temperature) ^b	X		X	Predose, 1, 2, 4, 8 and 12 hours postdose	X
12-Lead ECG ^c	X			Predose, 1, 4 and 12 hours postdose	X
Clinical Laboratory Evaluations	X		X		X
AE and Concomitant Medication Monitoring	X	X	X	Predose, 1, 2, 3, 4, 6, 8 and 12 hours postdose	X
Plasma Concentration Assessments					
Blood Sampling				Predose, pre-capsaicin and 2 hours post capsaicin	

Pharmacodynamic Assessments					
Intradermal Capsaicin Injection		X ^d	X ^e	X ^f	
Pain Measurement		X ^g	X ^h	X ^h	

Abbreviations: AE – adverse event; BP – blood pressure; ECG – electrocardiogram; GABA – Gabapentin; HR – heart rate; KLS - Ketoprofen Lysine Salt SARS-CoV-2 – severe acute respiratory syndrome coronavirus 2.

a A full check of inclusion/exclusion criteria will take place at screening. At all other days to which inclusion/exclusion criteria apply, only those particular inclusion/exclusion criteria will be checked

b Supine only.

c ECG assessments will be conducted within a ±30 minute time window.

d Additional screening visit at least 7 days prior to dosing to determine response to capsaicin and vehicle injections

e At a similar time of day to that anticipated on Day 1

f At estimated T_{max} for KLS alone or KLS-GABA from Part A

g Pain VAS, Flare, Hyperalgesia, Allodynia conducted pre-capsaicin injection and 15 minutes post injection.

h Pain VAS, Flare, Hyperalgesia, Allodynia conducted pre-capsaicin injection and 15, 30, 60, 90 and 120 minutes post injection

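### SAP 3's fallback for dosing-day records with neither a time nor a pre-dose label could class a post-dose vital sign or ECG as pre-dose and let it into baseline

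*SAP*

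**What the plan says.** The rule is one sentence in SAP 3 (Conventions). Its trigger has two parts, both of which must hold: it covers "Assessments on the day of the dosing where neither time nor a nominal pre-dose indicator are captured". Its action is that these records "will be considered prior to the dosing if such procedures are required by the protocol to be conducted before the dosing". The test is whether the protocol requires the procedure before dosing, not whether the procedure is confined to that time.

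The same section defines baseline. For Part B safety endpoints, "the last observation before dosing will be considered the baseline measurement unless otherwise specified"; Part A uses the equivalent definition within each treatment period. SAP 6.6.2 and 6.6.3 then summarise ECG and vital signs as change from that pre-dose baseline.

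Both procedures are scheduled on each side of dosing:

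- Part A vital signs (Protocol Appendix 1): "Predose, 1, 2, 4, 8, 24 and 48 hours postdose"
- Part A ECG (Protocol Appendix 1): "Predose, 1, 4, 24 and 48 hours postdose"
- Part B vital signs (Protocol Appendix 2): "Predose, 1, 2, 4, 8 and 12 hours postdose"
- Part B ECG (Protocol Appendix 2): "Predose, 1, 4 and 12 hours postdose"

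On ECG replication, the protocol's ECG section (7.2) states: "The 12-lead ECG will be collected in triplicate, approximately 1 minute apart, at Screening, and within approximately 1-hour predose". All other ECG timepoints are single readings unless a finding is abnormal.

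**The concern.** The inference behind the rule is sound when a procedure happens only before dosing on that day: an unlabelled record must then be the predose one. Part A laboratory tests fit this, since they are taken predose and next at 48 hours. For vital signs and ECG the condition is met by every Day 1 record, so it carries no information about when the record was taken. In Part B, laboratory tests are on Day -1, and both safety measurements scheduled on Day 1 (vital signs and ECG) continue after dosing.

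The wording has a second gap. Read literally, a record labelled as a post-dose timepoint but missing its clock time has no time and no pre-dose indicator, so it also qualifies.

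At stake is an on-drug value being treated as drug-free. If it enters baseline, any drug effect in it is subtracted from that subject's change scores. The SAP leans the other way for adverse events: under SAP 7.2, a missing start day whose default would precede treatment is moved to the treatment start date, which makes the event treatment-emergent.

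**Working it through.** The plan states no figure on this point, so there is none to reproduce. The check counts how often the rule's label could be wrong, then what a wrong label does to baseline.

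**Step 1. Share of Day 1 timepoints that are post-dose.** Dosing is in the morning of Day 1, so the 12-hour time falls on Day 1 and the 24- and 48-hour times do not. Share = post-dose timepoints / all Day 1 timepoints.

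| Measurement | Day 1 timepoints | Post-dose share |
|---|---|---|
| Part A vital signs | predose, 1, 2, 4, 8 h | 4/5 = 80% |
| Part B vital signs | predose, 1, 2, 4, 8, 12 h | 5/6 = 83% |
| Part A ECG | predose, 1, 4 h | 2/3 = 67% |
| Part B ECG | predose, 1, 4, 12 h | 3/4 = 75% |

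**Step 2. The same for individual ECG recordings.** With three predose recordings and one at each later time, share = post-dose recordings / (post-dose recordings + 3).

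- Part A: 2/(2 + 3) = 2/5 = 40%
- Part B: 3/(3 + 3) = 3/6 = 50%

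This ignores extra triplicates after an abnormal finding. Either set of shares is an error rate for the label only if a record lacking both items is equally likely to be any of those counted. The documents neither support nor contradict that assumption.

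**Step 3. Effect on one subject's baseline.** Let p be the true predose value, s the stray post-dose value and d = s − p.

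- ECG: SAP 6.6.2 averages multiple values at a timepoint. If s is pooled with three true predose readings averaging p, baseline = (3p + s)/4 = p + d/4. Baseline moves by a quarter of d, and each change score for that subject and period moves by −d/4.
- Vital signs: SAP 6.6.3 gives no averaging rule, and a record without a time cannot be ordered against a timed predose value, so which of the two is the last observation is undefined. The shift lies between 0 and d.
- Worst case for either: the shift is d, when there is no other predose value or the stray value replaces it.

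**Step 4. Effect on a group mean, assuming one affected subject and all subjects contributing.** Part B has 128/8 = 16 subjects per arm; Part A has 12 subjects per treatment.

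- Worst case: d/16 = 0.063d in Part B; d/12 = 0.083d in Part A.
- Pooled ECG: d/(4 × 16) = d/64 = 0.016d in Part B; d/(4 × 12) = d/48 = 0.021d in Part A.

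**Step 5. Reach.** SAP 3 takes Part B pharmacodynamic baselines from the matching Day -1 post-capsaicin timepoints, so the rule does not touch them or the Part B primary endpoint. The pharmacokinetic analysis is outside this SAP.

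**The case against.** The strongest reply is that this is a last-resort rule that may never be used. Protocol 11.1 sends missing or inconsistent eCRF entries to the investigator as queries, to be resolved before database lock, and keeps original ECG traces with the source. SAP 3 excludes unscheduled values from analysis. SAP 6.6.3 summarises vital signs by timepoint, and Protocol 10.5.2.3 and 10.5.2.4 summarise vital signs and ECG by treatment and time, so scheduled records should normally carry a label. The sentence can also be read as covering only the assessment that is itself required before dosing. Reclassifying a record plainly labelled post-dose would contradict the rest of the plan. The affected summaries are descriptive, and SAP 3 rules out hypothesis testing.

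All of this stands as a limit on size and likelihood. None of it corrects the sentence: the SAP provides for records that still lack timing, and its wording can misplace them.

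A reader might infer more than the documents support:

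- *That every Day 1 vital sign or ECG without a clock time will be called pre-dose.* The rule also needs the pre-dose indicator to be absent, and the wording allows narrower readings.
- *That most ECG recordings at risk are post-dose.* This is true of timepoints, not of recordings (40% and 50%).
- *That the rule empties the true post-dose cell.* A record with no time and no label cannot be placed in a post-dose cell under any rule. Only a record with a post-dose label and no time, on the literal reading, would be lost from its cell.
- *That baseline is wrong by the full post-dose change.* That is the worst case in Step 3.

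**Conclusion.** The concern holds as a minor wording defect. For procedures repeated after dosing on Day 1, the SAP's test cannot tell a predose record from a post-dose one, yet it resolves the doubt in favour of pre-dose. A post-dose vital sign or ECG lacking both a time and a pre-dose indicator could therefore enter that subject's baseline.

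For an affected subject, the shift runs from none, through a quarter of the difference for an ECG pooled with a complete triplicate, to the full difference in the worst case. With one affected subject, a group mean moves by at most about 6% (Part B) or 8% (Part A) of that subject's difference. The documents give no count of such records, and after queries it may be zero, so the likely effect on reported results is very small or nil. Only descriptive change-from-baseline safety summaries are exposed. Safety is a secondary endpoint in both parts, which is reason enough to tidy the sentence but not to rate it higher.

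**What to change.** Amend the sentence in SAP 3 in three respects before programming:

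1. Limit the rule to procedures that the protocol schedules only before dosing on that day.
2. For procedures scheduled both before and after dosing, assign the record by its nominal timepoint when the clock time is missing.
3. If both the time and the nominal timepoint are missing, list the record only and do not use it as baseline.

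The cost is a short SAP clarification, with no change to study procedures or data collection. The downside is that a few records that cannot be placed in time, if any exist, move from the summaries to the listings.

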Abnormal laboratory findings (e.g., clinical chemistry and haematology) or other abnormal assessments (e.g., ECGs, vital signs) that are judged by the Investigator as clinically significant will be recorded as AEs or SAEs if they meet the definition of an AE or SAE. Clinically significant abnormal laboratory findings or other abnormal assessments that are detected during the study or are present at baseline and significantly worsen following the start of the study will be reported as AEs or SAEs. The Investigator will exercise his or her medical and scientific judgment in deciding whether an abnormal laboratory finding, or other abnormal assessment is clinically significant. Liver chemistry thresholds have been designed to assure subject safety. When subjects meet the hepatic transaminase threshold criteria (AST or ALT $\geq 3 \times$ ULN), the subject should undergo close observation, including monitoring for symptoms (clinical symptoms of hepatitis, or hypersensitivity, fatigue, decreased appetite, nausea, vomiting, abdominal pain, jaundice, fever, or rash) and hepatic function (AST, ALT, alkaline phosphatase [ALP]), and fractionated bilirubin at least every 48 hours, until symptoms and/or hepatic function abnormalities resolve, stabilise, or return to baseline values. This event should be reported to Dompé within 24 hours of learning of its occurrence. [Appendix 4](#) represents the decision tree for whether or not study medication will be discontinued. A specialist or hepatology consultation should be considered in cases of protocol-mandated study medication discontinuation.

In addition, every attempt should be made to obtain the following for any subject who meets the hepatic transaminase threshold criteria:

- Viral hepatitis including: hepatitis A immunoglobulin (IgM) antibody, hepatitis B surface antigen and hepatitis B core antibody (IgM), HCV RNA, cytomegalovirus IgM antibody, Epstein-Barr viral capsid antigen IgM antibody (or if unavailable, obtain heterophil antibody or monospot testing), and hepatitis E antibody (if subject resides outside UK or has travelled outside UK in past 3 months).
- Serum creatine phosphokinase and lactate dehydrogenase. Record the appearance or worsening of clinical symptoms of hepatitis, or hypersensitivity, fatigue, decreased appetite, nausea, vomiting, abdominal pain, jaundice, fever, or rash as relevant on the AE report form.

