10.5.2.2. Clinical Laboratory Evaluations

Clinical Laboratory evaluation results will be listed and compared to laboratory reference ranges, with those values outside of the applicable range flagged as high (H) or low (L). The

quantitative laboratory data will be summarised using descriptive statistics for each parameter by treatment and time. Urinalysis data will be listed only. A summary of subjects reporting an abnormal value will be reported.

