1.2.4. Secondary Endpoints (Part B)

The secondary endpoints of the study are:

- Subjective rating of pain from the ID capsaicin model.
- Pain score of hyperalgesia from the ID capsaicin model.
- Area and pain score of brush-evoked allodynia from the ID capsaicin model.
- Area of flare (AF) from the ID capsaicin model.
- Plasma PK concentrations.
- Clinical safety data from AE reporting, 12-lead ECG, vital signs (supine blood pressure, heart rate, oral temperature), clinical laboratory evaluations (chemistry, haematology, urinalysis, and coagulation) and physical examinations in healthy male subjects.

Statistical Analysis Plan

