6.6.4. Clinical laboratory

Clinical Laboratory evaluation results (haematology and blood chemistry) will be summarised. Descriptive statistics will be calculated for absolute value and change from baseline (pre-dose) of each parameter by visit and by treatment according to treatment period. Categorical parameters (if applicable) will be summarised by counts and percentages of participants within each category by treatment group and visit. All presentations will be based on the International System of Units. The frequency of laboratory abnormalities will be tabulated.

Urinalysis data will be listed only. Clinical Laboratory listings will flag values that are outside normal reference ranges or markedly abnormal findings.

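### The SAP plans no summary of coagulation and does not declare the omission, and its unrestricted rule on unscheduled values can drop a subject from the safety abnormality tables

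*SAP*

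**What the plan says.** **Coagulation.** SAP 1.2.4 lists among the Part B safety endpoints "clinical laboratory evaluations (chemistry, haematology, urinalysis, and coagulation"; SAP 1.2.2 does the same for Part A. Protocol 10.5.2 names coagulation as one of the laboratory safety panels, and Protocol Table 4 lists the tests: prothrombin time, international normalised ratio and activated partial thromboplastin time. Protocol 10.5.2.2 plans descriptive statistics of the quantitative laboratory data, parameter by parameter, and reserves listing-only treatment for urinalysis. SAP 6.6.4 says "Clinical Laboratory evaluation results (haematology and blood chemistry) will be summarised", also makes urinalysis listing-only, and adds "The frequency of laboratory abnormalities will be tabulated". It does not mention coagulation. SAP 8 declares one change from the protocol, to the Part B primary endpoint.

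**Unscheduled values.** SAP 3 says "Unscheduled values will not be used for analysis" and then "Assessments conducted at unscheduled visits will be listed". It also says of the listings that they "will include all available data including unscheduled data". SAP 6.6.3 plans frequency tables of vital-sign abnormalities by visit and timepoint, and SAP 6.6.4 plans the laboratory equivalent. Neither section brings unscheduled values back. Protocol 10.5.2.2 says "A summary of subjects reporting an abnormal value will be reported", without stating which values count. Protocol 7.1 allows extra tests after abnormal values. Protocol 7.5.1.5 requires, once AST or ALT reaches 3 times the upper limit of normal, liver tests including "fractionated bilirubin at least every 48 hours, until symptoms and/or hepatic function abnormalities resolve".

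**The concern.** Excluding unscheduled values from by-visit means is normal practice, because those summaries need a common set of timepoints. An abnormality table answers a different question: how many subjects in each arm had an out-of-range result after dosing. For that question an unscheduled result is as informative as a scheduled one, and the SAP sentence makes no distinction between the two uses.

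The coagulation gap is simpler. A measured component of a secondary endpoint, which the protocol plans to summarise, appears in the SAP only in the endpoint definitions and in no analysis section.

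The stake is the completeness of the safety tables for a product that, by Protocol 1.4, has no earlier clinical data, and for which Protocol Table 3 names gastrointestinal bleeding as a risk. A listing preserves each result but gives no incidence by arm.

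**Working it through.** The plan gives no figure on this point, so the check is a comparison of texts and a count of scheduled visits.

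**1. Panels: endpoint against analysis.**

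| Panel | SAP endpoint (1.2.2, 1.2.4) | Protocol 10.5.2.2 | SAP 6.6.4 |
|---|---|---|---|
| Haematology | named | summarised | summarised |
| Chemistry | named | summarised | summarised |
| Urinalysis | named | listed only | listed only |
| Coagulation | named | summarised, as quantitative laboratory data | not mentioned |

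Of four panels, two are summarised, one is expressly listed only in both documents, and one is left without an analysis. The omission from the descriptive summaries follows directly from the bracketed panel names in SAP 6.6.4. The omission from the abnormality table is an inference: that sentence names no panel, and the only panels under discussion in the section are haematology, chemistry and urinalysis.

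**2. Which subjects the unscheduled rule can remove.** Take one laboratory parameter and one subject after dosing.

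- Scheduled value abnormal, unscheduled repeats abnormal: the subject is counted. Only a worse value on the repeat is lost.
- Scheduled values normal, an unscheduled value abnormal: the subject is not counted.
- No abnormal value: the rule has no effect.

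Only the second case changes a count of subjects. The two protocol sources of extra tests (7.1 and 7.5.1.5) both start from an abnormality already found, so they mostly produce the first case. If the table is laid out by parameter, which the SAP does not state, the second case can also arise within a triggered liver panel. For example, AST could be abnormal at a scheduled visit and bilirubin only on a later unscheduled sample.

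**3. Where the second case is most plausible.** Scheduled post-dose laboratory occasions, from the schedules of assessments:

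- Part A (Appendix 1): 48 hours post-dose in each of 2 periods, plus follow-up: 2 + 1 = 3.
- Part B (Appendix 2): Screening, Day -1 and follow-up, of which only follow-up, 5 to 7 days after dosing, is post-dose: 1.

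In Part B, any laboratory sample taken between dosing and follow-up is outside the schedule. If it is abnormal and the follow-up value is normal, the table does not show the subject. Vital signs are less exposed, since Part B schedules them at 1, 2, 4, 8 and 12 hours and at follow-up. However, the SAP 6.6.3 table is built by visit and timepoint, so it has no place for an unscheduled reading.

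**4. A conflict with the baseline definition.** SAP 3 takes the last observation before dosing as the Part B safety baseline. If a Day -1 test is repeated before dosing, the repeat is that last observation, yet the rule on unscheduled values, read literally, bars it.

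**5. ECG.** SAP 6.6.2 averages multiple ECG values at a timepoint and plans no ECG abnormality table, so the point does not extend to ECG.

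**The case against.** The best reply is that little is lost. Protocol 7.5.1.1 gives as an example of an adverse event a new laboratory abnormality that leads to withdrawal, treatment or further follow-up. Protocol 7.5.1.5 has clinically significant laboratory and vital-sign findings recorded as adverse events. These reach the treatment-emergent tables in SAP 6.6.1, and a subject withdrawn for such a finding appears in the disposition table (SAP 6.1). Listings keep unscheduled results, and SAP 6.6.4 flags out-of-range laboratory values in them. All of this stands, and it limits the point. It does not close it, because adverse event capture depends on the investigator's judgement of significance and listings carry no incidence by arm.

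It can also be said that the protocol never requires unscheduled values in the abnormality summary, and that it plans no abnormality table for vital signs at all. That is correct. The unscheduled rule is therefore not shown to be a departure from the protocol that SAP 8 should have declared; only the coagulation omission is. The term unscheduled is also undefined, and the table shells are in a separate document (SAP 9) that may settle some of this.

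Mixing unscheduled values into a table gives subjects with repeat tests more chances to show an abnormality. That is a real cost, and a footnote can state it.

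A reader might infer from the rule that the safety summary is biased towards no finding. The documents do not support this: a scheduled abnormal value is still counted, and the adverse event route covers the significant findings. A reader might also put the effect at 6 percentage points, because 128 / 8 = 16 per arm and 1 / 16 = 6.25%. That is only the weight of one subject, and nothing in the documents shows that a subject would be missed.

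**Conclusion.** Two limited defects stand.

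First, coagulation has no descriptive summary in the SAP although the protocol plans one, and SAP 8 is silent. This affects one of four laboratory panels in the safety endpoint of both parts. It is explicit for the descriptive summaries and inferred for the abnormality table.

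Second, SAP 3 read literally removes from the laboratory and vital-sign abnormality tables any subject whose only abnormal post-dose value was unscheduled. This is most plausible for laboratory tests in Part B, which has a single scheduled post-dose laboratory visit. How often it would happen cannot be derived from the documents, so no size beyond the individual subject is claimed.

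The second conclusion assumes that the rule applies to the abnormality tables as written and that the separate shells do not override it. Both defects should be corrected because the edits are short and need no change to study conduct.

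**What to change.** 1. In SAP 3, restrict the exclusion of unscheduled values to post-baseline by-visit descriptive statistics, and define unscheduled, including the status of a repeat taken within a scheduled visit. Limiting the rule to post-baseline statistics also removes the conflict with the baseline definition.
2. In SAP 6.6.3 and 6.6.4, add a subject-level count, by treatment, of subjects with any post-dose abnormality, based on all scheduled and unscheduled values. Add a footnote that subjects with repeat tests had more opportunities to show an abnormality.
3. In SAP 6.6.4, add coagulation to the panels summarised and to those in the abnormality table, or declare and justify its omission in SAP 8.

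The cost is a few SAP sentences and one extra table per domain. The data are already planned for collection and listing, so no visit, sample or procedure changes.
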